- c. **To identify key factors (alcohol and drug use, social support, psychological distress, quality of life) that predict re-arrest and nights spent homeless using traditional and smart phone-based assessment approaches.** It is hypothesized that key variables that are measured in- person (e.g., alcohol/drug use, perceived social support, psychological distress, quality of life) and via daily phone-based assessments (e.g., affect, stress, discrimination, alcohol/drug use) will have direct effects on re-arrest and number of homeless nights. These key variables are also hypothesized to mediate the relation between treatment condition and number of homeless nights and re-arrest.

Study Design:

This study is a 3-arm randomized controlled trial. Specifically, male and female homeless adults who enroll in a shelter based homeless recovery program following release from either the Dallas County Jail or the Dallas City Jail (N=462) will be randomized to one of three conditions: Usual Case Management (UCM); Usual Care plus Smartphone (UCM+SP); or Usual Care plus Smartphone based Case Management (SPCM). SPCM will be delivered through a modified version of the PI's previously developed smartphone application (i.e., "app") on a study provided smartphone. The app will not provide case management and crisis intervention services directly; rather, it will prompt twice weekly contact with their case manager and provide links to service providers through the touch of a button. Primary study outcomes are service utilization, number of homeless nights, and re-arrest. Another key focus of this study is to address gaps in our understanding of the factors that drive re-arrest and homelessness by using traditional in-person (i.e., baseline, 1, 3, and 6 months post- baseline) and smartphone based (i.e., daily for 6 months) assessment methods to identify distal and proximal predictors of continued homelessness and arrest. Arrest records will be examined to determine if participants are re-arrested within 12 months of study enrollment.

Participants who are randomly assigned to the UCM+SP or SPCM conditions will receive a smartphone at the randomization visit and they will be asked to carry it with them at all times for 6 months (26 weeks). Date, time, location, and duration of SPCM app feature use (e.g., case manager calls) will be recorded by the app for future analysis. See Table 1 for a summary of study conditions.

Study Conditions

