Participants have reported few problems using the QDS program, including those with no computer experience. Staff will be available to help participants who may have difficulty. The amount of time needed to complete the QDS administered questionnaires varies by study visit. Based on our previous experience with collecting data in homeless adults we estimate that the baseline visit will require approximately 1-2 hours to complete and follow-up assessment visits will require approximately 1-2 hours. Note that although breaks have been encouraged in our previous studies that have used QDS assessments in this homeless population, none actually took breaks. Examples of traditional measures are listed in Table 2 and include multiple constructs that are hypothesized to directly and indirectly (i.e., mediation of the treatment effect) affect the study outcomes. In addition, barriers to phone-based case management sessions and staff and participant perceptions of the SPCM app will be assessed.

See Appendix A for measure descriptions, assessment items, and a schedule that indicates which measures will be administered at each visit. In addition to the QDS System, assessment data may be collected through the REDCap system. REDCap is a secure web application for building and managing online surveys and databases and is specifically tailored for the management and administration of online data collection for research studies.

Alcohol/drug use, re-arrest, and number of homeless nights will be collected using a Timeline Follow-back procedure (See Appendix) at all 1, 3, and 6-month follow-up visits. In addition, arrest data from the Dallas County Jail and the Dallas City Jail will be examined to identify participants who are re-arrested within 12- months of the randomization visit (see **Director of Criminal Justice Letter of Support**). This will provide an objective measure of the date and time of arrest as well as a description of the offenses that occurred. The research team will share participant's name and date of birth to obtain this information, but no additional information that the participant provides to us over the course of the study will be shared with this Dallas County employee or the Jail. For participants who complete online surveys via REDCap, the participant will be instructed to call the research team to complete the Time Line Follow Back for location, drug and alcohol use.

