Ecological Momentary Assessment Measures (EMA; phone based). EMA is currently the most accurate way to measure phenomena in near real-time in natural settings.^{42,44} Thus, EMA methodology will enable the identification of key variables that predict study outcomes with less bias than traditional in-person

Table 2. In-person assessment measures

Demographics/Background
Demographic Information Questionnaire
Homelessness Questionnaire
Arrest History ⁵¹
Health, Mental Health, & Health Behavior
Patient Health Questionnaire ⁵² (depression/anxiety/alcohol)
Mental Health Component from the SF-12 ⁵³
Health Related Quality of Life ⁵⁴
Alcohol and Drug Timeline Follow Back ⁵⁵
88 COVID-19 Vaccine
Common Measures for Adult Well-Being ⁵⁶
Stress/Stressor Measures
Discrimination ⁵⁶
Urban Life Stressors Scale ⁵⁷
Personal Victimization ⁵⁸
Perceived Stress Scale – Short Version ⁵⁹
Negative Affect
Aggression ⁶⁰
Positive and Negative Affect Schedule ⁶¹
Loneliness Scale ⁶²
Interpersonal/Intrapersonal Resources
Interpersonal Support Evaluation List-12 ⁶³
Religious Participation

assessments. At the randomization visit, those assigned to the UCM+SP and SPCM conditions will be trained on how to use the smartphone to complete EMAs and how to use the “Call Study Staff” and “Payment” button/options. Those assigned to the SPCM condition will be trained to use the features of the full smartphone app. All participants who receive smartphones will be prompted by the phone to complete one EMA 30 minutes after waking each day for 6 months beginning the day after the randomization visit. After completion of the EMA, a joke or link to a joke will be presented to the participant via the smartphone. EMA data, collected over a 6-month period, will be used to identify key risk and protective factors that significantly impact substance use, re-arrest (i.e., re-arrest rates tend to peak within 6-12 months of jail discharge⁶⁷), and continued homelessness (homeless episode duration peaks at 180-190 days;^{68,69} see Aim 3).

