EMA Assessments. The EMA methodology that will be used in this study is similar to that developed by Shiffman and colleagues^{43,70,71} and was used in our previous studies. EMA items will assess multiple constructs that are hypothesized to be related to the study outcomes (see examples in Table 3). The phone will audibly and visually cue EMAs for 5 minutes, 30 minutes after each participant’s self-reported usual waking time. If the participant does not respond to the EMA prompt, the EMA will be recorded as missed and another prompt will be pushed later that day (this will reduce the likelihood of missed EMAs). EMAs will take approximately 2-4 minutes to complete. All EMAs will be date and time stamped for future analyses. Daily EMA items will ask about current affect and stress. In addition, participants will be asked a number of questions about the prior day that are hypothesized to be related to study outcomes (see Table 3). On Mondays, the daily EMA items and additional items will be assessed. Additional Monday items will cover topics/variables that have less day to-day variability (e.g., arrest; witnessing crimes or violence; emergency room visits; hospitalization; quality of life). Examples of EMA constructs that will be assessed are listed in Table 3 and actual EMA items are included in table

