Aim 3. The detectable effects for analyses based on a complete EMA sample size of 201 participants (allowing for 30% study drop-out; see [name] and Rosenheck³ for follow-up rates in a sample of homeless adults with both serious mental illness and substance abuse), 2-sided tests, alpha=.05, and power=.80 are presented in Table 8. Where appropriate, these estimates account for the fact that repeated observations from the same person will be correlated. The most conservative detectable effects for the GLMM EMA analyses will be presented. Thus, calculations are based on an N of 201 individuals completing 80% of 183 assessments during the 6-month EMA study period for a total of 29,426 EMAs across all participants. Since few EMA studies have been conducted in this population, we computed detectable effects using a reasonable range of intraclass correlation coefficient (ICC) values. Detectable effects estimates depend on the variance inflation factor (VIF)¹³⁴ which is based on both the size of the ICC and the average number of observations per person. The VIFs used to calculate the effective sample size are displayed in Table 8. Thus, using the EMA data, we will be able to detect factors that predict reductions in homeless nights by as little as 3.1 percentage points.

Analyses. Logistic Regression of traditional in-person assessments (e.g., substance use, social support, psychological functioning, quality of life; see Table 7 for other key constructs) and summarized EMA data (e.g., affect, stress, discrimination, alcohol and drug use) will be conducted to identify significant demographic, psychosocial, environmental, and behavioral predictors of re-arrest in the 12 months following the randomization visit (binary outcome). Covariates may include treatment group, age, gender, race/ethnicity, education, type of crime, and other variables as appropriate. Change scores (e.g., change in social support from baseline to the 1-month follow-up visit) will also be examined as potential predictors of re-arrest.

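### Aim 3 relates 12-month re-arrest to EMA summaries collected inside the same 12 months and does not require them to precede the first re-arrest

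*Combined protocol and SAP*

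**What the plan says.** The Aim 3 analysis text (Statistics) plans a logistic regression to find "behavioral predictors of re-arrest in the 12 months following the randomization visit (binary outcome"). Its candidate predictors are in-person assessments, EMA summaries and change scores; on the EMA part it reads "summarized EMA data (e.g., affect, stress, discrimination, alcohol and drug use) will be conducted to identify significant demographic, psychosocial, environmental, and behavioral predictors". The period that an EMA summary covers is not defined.

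The EMA section starts the daily assessments the day after randomization and states that "EMA data, collected over a 6-month period, will be used to identify key risk and protective factors that significantly impact substance use, re-arrest". Study Design likewise names "smartphone based (i.e., daily for 6 months) assessment methods to identify distal and proximal predictors of continued homelessness and arrest".

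Arrest dates are available. The two Arrest data paragraphs (Sources of Materials; Data handling) have them recorded, used to decide whether a re-arrest falls within 12 months of randomization, and merged into the master dataset.

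The plan expects some data from people who have already been re-arrested. In EMA Assessments, "Additional Monday items will cover topics/variables that have less day to-day variability (e.g., arrest; witnessing crimes or violence"). Under Traditional Measures, "Alcohol/drug use, re-arrest, and number of homeless nights will be collected using a Timeline Follow-back procedure" at each follow-up visit. Participant Retention, on the other hand, allows phone service to end after a run of missed EMAs without contact.

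No section sets a landmark, a lag, a cut-off at arrest or a time-to-event model for re-arrest. The day-level mixed model concerns homeless nights.

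**The concern.** A predictor of an event should be measured before the event. Here the predictor window lies inside the outcome window, so a person re-arrested in month 2 can contribute EMA data from months 3 to 6 to the summary that is meant to predict that arrest. There are two routes to a false finding:

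- **Arrest changes later reports.** If stress, affect or substance use shifts after arrest, a consequence is read as a predictor.
- **Arrest ends the reports.** The summary then covers a shorter, earlier period in arrested people. Totals are biased, and so are means if the measure trends over time.

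The Objectives hypothesize that the EMA variables directly affect re-arrest. The written model cannot separate that from an effect in the other direction.

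**Working it through.** **1. The plan's own figure.** The Aim 3 EMA base reproduces: 201 × 0.80 × 183 = 29,426.4, stated as 29,426. N = 201 follows from 2 × 144 × 0.70 = 201.6. Neither figure is disputed here; 201, 183 days and 80% completion are used below.

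**2. Overlap.** EMA covers days 1–183 of a 365-day outcome window: 183/365 = 50%.

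**3. First re-arrests before month 6.** The EMA section says "re-arrest rates tend to peak within 6-12 months of jail discharge", so arrests are taken as back-loaded: F(t) = 1 − exp(−ln 2 × t^k), t in years, with F(1) = 50% (assumed; Background Information says more than half for Texas county jails). Shapes k = 1.5 and 2 peak at 7.4 and 10.2 months.

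- k = 1.5: F(0.5) = 1 − exp(−0.693 × 0.354) = 0.217; 0.217/0.5 = 44% (43.5%).
- k = 2: F(0.5) = 1 − exp(−0.693 × 0.25) = 0.159; 0.159/0.5 = 32%.

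With 40% re-arrested, the shares are (1 − 0.6^0.354)/0.4 = 41% and (1 − 0.6^0.25)/0.4 = 30%. With 60% they are (1 − 0.4^0.354)/0.6 = 46% and (1 − 0.4^0.25)/0.6 = 34%. If the clock starts at discharge, up to 60 + 14 = 74 days before randomization, refitting to 50% gives 49% and 40%.

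**4. False positives of a null EMA predictor.** Simulation: 4,000 trials per cell, N = 201, 183 days, 80% completion, total daily SD 1, ICC 0.4 (assumed). The 6-month EMA mean enters a logistic model of 12-month re-arrest, tested at 5%. Those who resume do so 14 days after arrest.

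| Scenario | k = 1.5 | k = 2 |
|---|---|---|
| 0.5 SD shift after arrest, all resume | 13.2% | 8.4% |
| Same, half resume | 6.5% | 5.8% |
| Same, a quarter resume | 4.6% | 5.1% |
| EMAs stop at arrest, no trend | 4.1% | 5.1% |
| EMAs stop, 0.5 SD trend over 6 months | 7.1% | 6.3% |
| EMAs stop, 1 SD trend | 15.4% | 9.2% |

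Separately written simulations agreed: 14% / 8–10% in row 1 (the 10% came from a run without the 14-day gap), 7–8% / 6% in row 2, 8% / 6% in row 5 and 17–18% / 9–10% in row 6.

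Row 1 moves with its assumptions. A 0.25 SD shift gives 6.6% / 5.8% and a 1 SD shift 41.2% / 18.1%. At 0.5 SD, ICC 0.2 gives 23.2% / 12.0% and ICC 0.6 gives 12.4% / 7.0%.

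**5. One-month change scores.** With a 0.5 or 1 SD shift: 5.4–6.2% (k = 1.5) and 5.2% (k = 2).

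**6. The remedies.** With a 1 SD trend plus a 1 SD post-arrest shift and everyone resuming, the 30-day landmark gave 4.4% / 5.0%. A Cox model with EMA to date, carried forward after month 6, gave 4.3% / 4.9%. Power for a true hazard ratio of 1.35 (exp 0.3) per between-person SD:

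| Model | k = 1.5 | k = 2 |
|---|---|---|
| Full-window logistic | 82% | 83% |
| Time-varying Cox, carried forward | 84% | 85% |
| 30-day landmark | 79% | 81% |

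The landmark leaves out F(30/365)/0.5 = 3% / 1% of 12-month first re-arrests, or up to 7% / 4% with the clock at discharge.

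**The case against.** The strongest defence is that silence is not a choice. The summary window is undefined, so the analyst could cut it at arrest, and several plausible scenarios show little or no inflation. The second part stands: with a quarter resuming, or with EMAs stopping and no trend, the error rate stays near 5%. The first part does not rescue the text, because the plan assigns EMA from the whole 6 months to re-arrest and gives no rule for ordering.

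A reader might also infer more than the documents support:

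- **That arrest dates go unused.** They are used to classify re-arrest within 12 months. What is missing is their use to order predictors against the first re-arrest.
- **That the error rises about fourfold.** A rate of 20% arises for a 6-month visit value with a 0.5 SD shift, k = 1.5 and half of those already re-arrested attending. Study Design does name "traditional in-person (i.e., baseline, 1, 3, and 6 months post- baseline) and smartphone based (i.e., daily for 6 months) assessment methods" in general terms, but the only follow-up visit that the Aim 3 analysis text names for re-arrest is month 1, in a change score.
- **That a third or more of null predictors would be declared.** For a 0.5 SD shift with everyone resuming, that requires a constant hazard, which does not fit the late peak that the plan cites.
- **That false predictors would feed future interventions.** That sentence in the plan concerns homeless nights.
- **That the nightly housing model has the same fault.** No error rate was established for it, and the daily EMA also collects prior-day exposures.

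Arrest being a primary outcome variable does not make this predictor analysis a primary one.

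**Conclusion.** The concern holds for EMA predictors of re-arrest. As written, the model can let post-arrest EMA data, or the early end of EMA data, act as a predictor of the arrest. Under the stated assumptions the false-positive rate is about 8–14% for a 0.5 SD post-arrest shift with everyone resuming and 6–8% with half resuming. If EMAs stop at arrest, it is about 5% with no trend, 6–8% with a 0.5 SD trend and 9–15% with a 1 SD trend (up to 18% in repeat runs). The documents give none of the resumption rate, shift, trend, ICC or hazard shape, so these figures show a range and are not a forecast.

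The concern extends to 3- or 6-month visit values only if they are used as predictors. One-month change scores are hardly affected. Baseline predictors and the randomized comparisons are not affected. This should be corrected, but it does not threaten the trial's main comparisons.

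**What to change.** In the Aim 3 analysis text, keep the logistic model for baseline predictors. For EMA predictors, use only data from before the first re-arrest, by one of two routes:

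- **(a)** Model time from randomization to first re-arrest, with the EMA mean or rate to date as a time-varying covariate, and state how values are carried forward after month 6.
- **(b)** Use a 30-day landmark: summarize EMA to day 30, count arrests after day 30, and report how many earlier arrests are left out. State that these people leave this predictor analysis only, since the Statistics section includes all randomized participants.

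If a follow-up visit value is used, count only arrests after the actual date of that visit. This follows from the same ordering rule but was not simulated. Avoid a 6-month landmark: it would leave about 57 (k = 1.5) or 69 (k = 2) of 100 events and 57% or 67% power.

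Cost: SAP wording and some programming on data already planned for collection. Route (a) lost no power in the check but relies on values up to 6 months old, which dilutes a short-lived effect. Route (b) loses 1–3% of events (up to 7%) and 2–3 points of power.

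A minor alignment: the 12 months start at the baseline visit in Subject Duration and at enrollment in Study Design, but at randomization in Traditional Measures, the Aim 3 analysis and Data handling. Use one start throughout.

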
Background Information:

At least 1.5 million people experience homelessness each year in the United States (US) and 6.2% of US adults have been homeless at some point in their lifetime.² Homeless adults are more likely to be male, single, and African American,¹ and have average life expectancies that are 8 (women) to 13 (men) years shorter than domiciled adults.³ Homeless adults are more likely to spend time in jail than domiciled adults,⁴ and as many as 32% of jailed adults report being homeless in the year prior to their arrest.^{4,5} Further, homeless adults are more likely to return to jail after incarceration than domiciled adults.⁶ In Texas, more than half of adults released from county jails are re-arrested within one year,⁷ and many of those re-arrested are homeless.⁸ In the Dallas County

Jail alone, 5530 homeless adults were incarcerated in 2013 at an estimated cost of \$12,557,406.⁹

Incarcerated homeless adults have a variety of risk factors that increase the likelihood of re-arrest. For instance, homeless inmates are more likely than domiciled inmates to have histories of mental illness and/or substance use disorders.^{4,8} Our own research has indicated that homeless adults released from jail in the past year were more likely than those not recently incarcerated to have a history of substance use and/or mental health problems.¹⁰ Thus, there is a strong need for mental health and substance abuse treatment among homeless adults following their release from incarceration. Studies have indicated that the link between homelessness and incarceration¹¹ can be attenuated through the use of case management services.¹²⁻¹⁴ The overall significance and scope of this issue was eloquently stated by Kushel and colleagues in their evaluation of the “revolving door” of homeless incarceration,¹¹ “High rates of imprisonment among homeless populations may be the end result of a system that does not provide access to timely services, including access to housing, health care, mental health care, and substance abuse treatment, and systems that have obstacles preventing receipt of these services by people exiting prison” (p. 1751). Thus, individuals who leave jail and return to the community without stable housing are at increased risk for premature mortality^{15,16} and re-arrest^{6,8} and are critically in need of interventions that increase access to services.

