All randomized participants will be included in the analyses and the trial will end once 462 participants are randomized and complete all study components. Preliminary data analyses, manuscript preparation, and conference presentations will begin in Year 2.

Aim 1. The number of participants ($n = 144$ in each group) was estimated based on the following assumptions: 1) random allocation of participants between 3 conditions; 2) type I error rate set to 0.05; 3) a 30% dropout rate for each condition;²³ 4) targeted minimum power of 0.9, and 5) a conservative increase of 4.5 case management sessions between the UCM and SPCM conditions across the 6-month study period. The estimated increase in in case management sessions is based on Lucht et al.,⁴⁹ which showed that 20% of all phone-based prompts to connect with an alcohol treatment counselor resulted in actual treatment sessions. Mondays, the daily EMA items and additional items will be assessed. Additional Monday items will cover topics/variables that have less day-to-day variability (e.g., arrest; witnessing crimes or violence; emergency room visits; hospitalization; quality of life). Examples of EMA constructs that will be assessed are listed in Table 3 and actual EMA items are included in the Appendix.

	Compensation (Usual Care)	Compensation (Smartphone Groups)
Visit 1 (Today)		
Questionnaire	\$30	\$30
Visit 2 (Within 3 Days)	\$30	\$30
Visit 3 (1-Month Follow-Up)		
Questionnaire	\$50	\$50
Phone Assessments	N/A	Up to \$50 every 15 days for survey completion (\$100)
Visit 4 (3-Month Follow-Up)		
Questionnaire	\$50	\$50
Phone Assessments	N/A	Up to \$50 every 15 days for survey completion (\$200).
Visit 5 (6-Month Follow-Up)		
Questionnaire	\$50	\$50
Phone Assessments	N/A	Up to \$50 every 15 days for survey completion (\$300).
TOTAL:	Up to \$210	Up to \$810

Analyses. Primary analyses for this aim will compare counts of the total number of case and crisis management sessions that occurred between the randomization visit and the 6-month follow-up across the 3 conditions using analysis of covariance (ANCOVA). Covariates may include race/ethnicity, age, sex, lifetime months homeless, type of arrest (e.g., violent vs. non-violent), substance abuse or mental health diagnoses,

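### Aim 3's change-score models for re-arrest do not require the same measure's baseline value, so a baseline effect can be reported as an effect of change

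*Combined protocol and SAP*

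**What the plan says.** The text is in the combined protocol and SAP, Statistics, Aim 3, Analyses. The method is "Logistic Regression of traditional in-person assessments (e.g., substance use, social support, psychological functioning, quality of life; see Table 7 for other key constructs"), together with summarized EMA data, to identify "predictors of re-arrest in the 12 months following the randomization visit (binary outcome"). The paragraph then adds: "Change scores (e.g., change in social support from baseline to the 1-month follow-up visit) will also be examined as potential predictors of re-arrest". On adjustment it says: "Covariates may include treatment group, age, gender, race/ethnicity, education, type of crime, and other variables as appropriate".

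Three features matter.

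- Examining change scores is a commitment, while the covariates are optional. Six are named and an open clause follows. The baseline value of the differenced scale is neither named nor ruled out.
- Levels of the same constructs are predictors in the same paragraph, but the plan does not say whether a level and its change enter one model.
- The third aim under Objectives hypothesizes that in-person measures such as social support and psychological distress act directly on re-arrest. The plan itself therefore expects levels to matter.

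By contrast, the Aim 2 analysis paragraph states as definite that baseline predictors of each outcome will be covariates.

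**The concern.** A change score is the 1-month value minus the baseline value, so it carries the baseline value with a minus sign. If it enters a model without its baseline, any association between baseline and re-arrest that the other covariates do not absorb is partly credited to change. Suppose people who start with more support are re-arrested less, and change in support is irrelevant. Those who start high tend to show smaller gains or losses, so gains in support would then look harmful.

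Re-arrest is one of the primary outcomes, and understanding what drives it is a stated focus of the study. A wrong sign on a modifiable factor would misinform later work. Because the plan leaves the specification open, two analysts following it could report different signs for the same factor, and the choice could be made after the results are seen.

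**Working it through.** **The plan's own figure.** No figure is given for the change-score analysis. The Aim 3 figure that can be rebuilt is "an N of 201 individuals completing 80% of 183 assessments during the 6-month EMA study period for a total of 29,426 EMAs": 201 × 0.80 × 183 = 29,426.4, and 2 × 144 × 0.70 = 201.6 gives the 201. Both reproduce. The point does not depend on them.

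**Inputs from the documents.**
- Two-sided alpha 0.05 ("2-sided tests, alpha=.05, and power=.80 are presented in Table 8").
- "a 30% dropout rate for each condition" (Aim 1), so 462 × 0.70 = 323.4, taken as n = 323; n = 201 is also tried.
- "In Texas, more than half of adults released from county jails are re-arrested within one year" (Background Information); 50% is the working event rate.

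**Assumptions not in the documents.** Baseline OR 0.67 or 0.80 per SD; baseline to 1-month correlation ρ from 0.3 to 0.9; SD ratio r = SD(1 month)/SD(baseline) from 0.8 to 1.5.

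**Step 1: what change-only imposes.** Let X0 be baseline, X1 the 1-month value, D = X1 − X0. The fuller model is βD·D + β0·X0 = βD·X1 + (β0 − βD)·X0. Dropping X0 sets β0 = 0, so the effects become +βD on X1 and −βD on X0: equal and opposite.

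**Step 2: size of the shift.** If the log odds depend on X0 only, with slope b per baseline SD, the slope on D alone is approximately b × (ρr − 1)/(1 + r² − 2ρr).
- r = 1: (ρ − 1)/(2 − 2ρ) = −0.5 for any ρ below 1.
- OR 0.67: b = ln 0.67 = −0.400, so the slope is +0.200. Simulated mean: +0.19 to +0.20.
- OR 0.80: b = −0.223, so the slope is +0.112. Simulated mean: +0.109 to +0.112.
- r = 0.8, ρ = 0.5: −0.6/0.84 = −0.714, so the slope is +0.286 at OR 0.67. Simulated: +0.289.

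**Step 3: when the sign reverses.** Reversal needs ρr < 1.
- r = 1.5, ρ = 0.7: 0.05/1.15 = 0.043. Simulated slope −0.02, significant in 5.7% of runs.
- r = 1.5, ρ = 0.9: 0.35/0.55 = 0.636. Simulated slope −0.25, the same sign as the baseline effect, significant in 38.5%.

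**Step 4: how often change is falsely significant** (1,000 simulated trials per setting; Monte Carlo standard error at most √(0.25/1000) = 1.6 percentage points). The effect is through baseline only; r = 1 unless stated.

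| Setting | ρ = 0.3 | ρ = 0.5 | ρ = 0.7 |
|---|---|---|---|
| OR 0.67, n = 323, change only | 51% | 42% | 25% |
| OR 0.67, n = 323, baseline added | 5.5% | 4.6% | 5.2% |
| OR 0.67, n = 201, change only | 39% | 25% | 18% |
| OR 0.67, n = 201, baseline added | 4.2% | 4.1% | 4.6% |
| OR 0.80, n = 323, change only | 22% | 17% | 11% |
| OR 0.80, n = 323, baseline added | 7.5% | 5.3% | 4.9% |

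With r = 0.8, ρ = 0.5, OR 0.67 and n = 323, change-only is significant in 64%. With no effect at all it is significant in 4.8%. With baseline added, the mean change coefficient lies between −0.008 and +0.007 in all six table settings.

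**Step 5: other structures** (n = 323, 50% events, OR 0.67, ρ 0.3/0.5/0.7).
- *Stable trait, measured with error at both visits.* D is then error only. Change-only is significant in 5.4%/4.8%/3.8%. With baseline added, the change coefficient is −0.17 to −0.21 and significant in 28%/30%/25%, because X1 given X0 is a second reading of the trait.
- *Only the 1-month level matters.* The change-only slope is b × (1 − ρ)/(2 − 2ρ) = 0.5b = −0.20: the right sign but half the size. Detection rises from 26–57% with change alone to 69–91% with both values fitted.

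**The case against.** The strongest reply is that the plan never says baseline is left out. The covariate list is permissive, its closing clause would admit baseline, and levels of the same constructs are already predictors in that paragraph. A reader might infer that Aim 3 tests change without baseline; the documents do not support that, and only the absence of a requirement can be shown. This part stands.

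Second, the high false-positive rates come from one assumed structure, in which only the observed baseline score matters. Under a stable trait with measurement error, change-only keeps about 5%, and it is the baseline-adjusted change term that becomes significant. This also stands. The rates are not a property of the plan, and adding baseline does not isolate a causal effect of change.

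Third, sign reversal is not universal; it fails when ρ × SD(1 month) exceeds SD(baseline). That is correct, though the same-sign case at r = 1.5, ρ = 0.9 shows that omission is not thereby made safe.

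Fourth, this is a supplementary sentence in an exploratory screen. That is true and limits the weight of the point.

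None of this defends leaving the specification open. Change-only is a special case of the model with both values, so fitting both loses no information. In the stable-trait case the two coefficients share a sign, which marks a level effect if both are reported.

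**Conclusion.** The concern holds as a gap in specification with a demonstrable consequence. The plan commits to change scores as predictors of re-arrest and does not require the baseline value beside them. If re-arrest depends on the baseline level, which Aim 3's own hypothesis makes plausible, a change-only model transfers part of that effect to change: minus one half of it when the SDs are equal, and with the sign reversed whenever ρ × SD(1 month) < SD(baseline).

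On the stated assumptions, false significance is about 25% to 50% at OR 0.67 and 11% to 22% at OR 0.80, against a nominal 5%. The odds ratios, correlations, SD ratios and the baseline-only structure are all assumptions, and under a stable trait with error the inflation disappears. A reader might take these rates as the trial's expected error rate, or conclude that the sign must reverse; the documents support neither. No randomized comparison and no sample size is affected.

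**What to change.** Add to the Aim 3 analysis paragraph: wherever a change score is a predictor of re-arrest, the baseline and 1-month values of that measure are fitted together (equivalently, change plus baseline), and both coefficients are reported. For changes to a later visit, use that visit's value in place of the 1-month value.

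State the interpretation in advance. The change term is the association of the later value with re-arrest given baseline, not the causal effect of changing. Coefficients of the same sign on both values indicate a level effect; clearly opposite signs are what a change effect would look like.

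The cost is one degree of freedom per predictor, using data already collected. Measurement error can still distort the change term, and the report should say so.
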